## Evaluating the Impact of an Emotion Regulation Intervention on Emotion Perception

### Purpose of the Study

**Aim 1:** To evaluate the short-term impacts of an emotion regulation intervention on emotion perception in the laboratory. In the laboratory training session, we will compare performance on behavioral emotion perception tasks between participants who receive the intervention, a training in an emotion regulation skill (i.e. mindful breathing), and participants in the control conditions (perspective-taking and worry inductions). **Hypothesis 1:** We predict that participants in the emotion regulation intervention condition will show less negative bias in their performance compared to participants in the control conditions. We also predict that intensity of emotional distress will be associated with negative biases.

**Aim 2:** To investigate the longitudinal effects of this intervention on emotion perception outside the lab using experience sampling. After the laboratory training session in aim 1, participants in both groups will receive an auditory reminder of the emotion regulation skill (a specific tone) three times a day through their mobile phones for one week and then will complete emotion perception tasks. Using our method of generalization, the participants in the intervention group have learned to associate the tones with reductions in emotional distress. For this aim, we will compare changes in performance on the emotion perception tasks over time between the three groups. **Hypothesis 2:** We predict that these cues will lead to greater decreases in negative biases in emotion perception over time compared to the control conditions. We will also test whether changes in emotional distress and regulation mediate the longitudinal changes in emotion perception performance.

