(1) Emotion Perception Bias Task (EPBT). This behavioral assessment is adapted from other studies investigating the effects of mood on emotion perception biases (Dyck et al., 2008; Schmid & Mast, 2010). In this task, participants will view photographs of people's faces expressing either a negative emotion (e.g. angry), positive emotion (e.g. happy). These photos will be displayed to participants one at a time for a brief period, and then asked to judge the emotion in a multiple-choice format (e.g. "happy" or "angry"). At the end of this task, participants are asked to rate how confident they were in the accuracy of their responses on a 0-100 scale.

(3) The Bell Lysaker Emotion Recognition Task (BLERT) (Bell, Bryson & Lysaker, 1997) measures the ability to identify affect cues. It is an audio-visual task designed to elicit a person's ability to discriminate seven emotional states (i.e. happiness, sadness, fear, disgust, surprise, anger or no emotion) given facial, voice-tonal and upper-body movement cues. The BLERT consists of twenty-one, 10-second vignettes (using the same male actor) containing one of three monologues involving a work related topic. After each vignette, the tape is paused and the participant circles the corresponding emotional label on an answer sheet. After identifying the emotion for each video, participants are asked to rate how confident

they were in the accuracy of their response on a 0-100 scale. Performance is indexed as the total number of correctly identified emotions (ranging from 0 to 21). Test scores include the total number of correct responses, the number of correct positive affect responses (happy and surprise), the number of correct negative affect responses (sadness and fear), the number of correct difficult responses and number of correct easy responses.

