#### Experimental Procedures

Intake Session: After determining eligibility, participants will complete measures of social and psychological functioning (DERS, IRI, PANAS-2, TMS, AIHQ-A, NIH SRS, PHQ-9, BES, EMT, SIAS, PFQ) and the two laboratory emotion perception tasks (BLERT, EPBT) through an online Qualtrics survey on a standard desktop computer in the laboratory. At this time, they will provide four recent stressful experiences for the personalized stressor task.

Training Session: All participants will come back to their lab for this session (ideally between 5-7 days after the intake session), which will take approximately 1.5 hours. First, all participants will be asked about: 1) current distress and suicidal urges (i.e. Suicide Risk Protocol), 2) any changes in medications since the previous visit, 3) nicotine, caffeine, and alcohol use that day, 4) subjective units of general psychological distress (SUDS; visual analogue scale from 1-9), 5) dissociation state, assessed using self-report (Dissociative-Tension States Scale 4 item version-DSS-4 from the DSS-acute), 6) levels of arousal with the Sedation Scale, and 7) current affect with the PANAS-2. Then, the experimenter will affix electrodes and will use Biopac MP150 hardware and AcKnowledge software for data acquisition. All participants will be assessed for baseline negative emotional arousal with psychophysiological (galvanic skin response) measures for five minutes. Then, participants will be randomized to one of three groups:

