Immediately after the emotional stressor task, all participants will again report: 1) subjective units of general psychological distress (SUDS; visual analogue scale from 0-9), 2) dissociation state, assessed using self-report (Dissociative-Tension States Scale 4 item version-DSS-4 from the DSS-acute), 3) levels of arousal with the Sedation Scale, and 4) current affect with the PANAS-2. They will then complete the laboratory emotion perception bias task and a manipulation check. Afterward, they will be oriented to the mobile phone prompts they will receive during the testing phase.

Testing Phase: During the one-week testing phase, participants in both conditions will receive three text-message prompts through their own phones randomly each day. These prompts will function both as an EMA measurement of self-reported negative emotional distress, as well as the delivery method of the tones. We will have a specific application, processed and stored on Heroku, that will receive and send text messages to participants via Twilio. In each prompt, participants will be asked to report on their current negative emotional distress (SUDS). When participants report high distress (i.e.,  $SUDS > 2$ ), they will automatically hear the tone by receiving a text message with an .mp3 file. The participants in the control conditions will also hear the tone despite having no previous associations with it, to control for potential placebo effects. After hearing this sound, participants will report again on

their distress, then complete the phone-based emotion perception task. As a manipulation check, the participants in the emotion regulation intervention condition will be asked if they actually used the mindful breathing skill. If the participant does not meet criterion for high distress, they will instead receive a text response on their phone thanking them for their response (see text message sample script document).

All participants will complete the laboratory emotion perception tasks and self-report measures of emotion and psychological functioning through an online Qualtrics survey at the end of this testing phase. They will also complete an exit questionnaire through this Qualtrics survey (see exit questionnaire document).

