Specific Aim 1: Aim 1 will determine if the emotion regulation intervention leads to fewer negative biases in emotion perception during the laboratory training session. For this aim, we will conduct ANCOVA analyses to study group differences in performance on the emotion perception laboratory tasks, controlling for their baseline scores assessed in the intake session. To compare the conditions' impacts on negative biases, we will analyze group differences in 1) number of trials with neutral facial expressions are misclassified as negative emotions; 2) accuracy for positive emotions and negative emotional expressions. We will also examine the relationship between emotional distress and emotion perception. Hypothesis 1: Participants in our emotion regulation condition will have less negative bias in emotion perception (e.g. fewer neutral faces misclassified as negative, lower accuracy for negative emotions, higher accuracy for positive emotions) compared to participants in both the control conditions. Even though the perspective-taking and mindful breathing conditions may have similar effects (e.g. increasing attention to social cues (Olsson et al., 2016; Quaglia, Goodman, & Brown, 2016)), perspective-taking inductions may still lead to mood-congruent biases by increasing negative emotional responses (Lamm, Batson, & Decety, 2007). Therefore, we predict that the emotion regulation intervention would reduce this bias significantly more than both the worry and perspective-taking conditions. We also predict that intensity of emotional distress will be related to negative biases in emotion perception.

Specific Aim 2: Aim 2 will compare the changes in emotion perception over time between the emotion regulation breathing condition and the control conditions. For this aim, Multilevel modeling (MLM) will be used because it permits evaluation of longitudinal data on participants over time with trajectories for each participant examined as random effects. We will conduct MLM analyses to study group differences in changes in the laboratory emotion perception tasks assessed during intake (time 1), the training session (time 2) and after the testing phase (time 3). For the phone-based behavioral task, we will first examine the psychometric properties of this measure in this clinical sample. Then, we will analyze group

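### Aim 1 lists a neutral-face measure that the training-session task is not described as providing, and no single bias score, or rule for conflicting scores, is tied to the 5% test

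*Combined protocol and SAP*

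**What the plan says.** All references are to the combined protocol and SAP.

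- **Measures.** Data Analysis & Statistical Considerations, Specific Aim 1, lists the "number of trials with neutral facial expressions are misclassified as negative emotions", then accuracy for positive and for negative expressions. Hypothesis 1 takes fewer neutral-to-negative errors, lower negative accuracy and higher positive accuracy as signs of less negative bias. The analysis is ANCOVA with the intake score as covariate.
- **EPBT content.** Measures and Tasks says participants see "faces expressing either a negative emotion (e.g. angry), positive emotion (e.g. happy") and are "asked to judge the emotion in a multiple-choice format"; the two example answers are one positive and one negative emotion.
- **BLERT content.** The other laboratory task asks participants to "discriminate seven emotional states (i.e. happiness, sadness, fear, disgust, surprise, anger or no emotion"). Its stimuli are audio-visual vignettes, not photographs of faces.
- **Timing.** At intake participants complete "the two laboratory emotion perception tasks (BLERT, EPBT) through an online Qualtrics survey". At training, after the stressor: "They will then complete the laboratory emotion perception bias task and a manipulation check". After the testing phase: "All participants will complete the laboratory emotion perception tasks and self-report measures of emotion and psychological functioning". Yet Aim 1 under Purpose of the Study states: "In the laboratory training session, we will compare performance on behavioral emotion perception tasks", in the plural, and Specific Aim 2 also treats the training session as time 2 for the tasks.
- **Test.** The 5% error rate, 80% power and f = 0.38 are attached to emotion perception bias as a construct. No score is named and no multiplicity rule is given.

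**The concern.** There are two linked problems.

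First, the first-listed Aim 1 measure needs neutral faces at training and again at intake for the covariate. The only task placed at training is not described as having them. The only stimuli described as emotionless belong to the BLERT, which the procedures do not place at training.

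Second, the primary question is bias, but the accuracies are not bias measures when taken one at a time. A participant who simply discriminates better scores higher on both valences. Hypothesis 1 would count the positive gain as less bias and the negative gain as more. Background & Significance gives some reason to expect such a change: it reports that strong negative emotion lowers sensitivity to others' expressions, and that brief mindful breathing can improve emotion perception. With three scores, no primary one and no rule for conflicting signs, the Aim 1 conclusion could be chosen after the data are seen.

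**Working it through.** **1. Sessions side by side**

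| Session | EPBT | BLERT |
|---|---|---|
| Intake | yes | yes |
| Training | yes | not named in the procedures; implied by the plural in Aims 1 and 2 |
| After testing phase | yes | yes (plural) |

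The neutral measure is therefore clear at training only if the EPBT contains neutral faces, which its description does not say.

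**2. The plan's power figure.** Three-group F test, N = 72, f = 0.38: noncentrality 0.38² × 72 = 10.4, df 2 and 69. Power is 0.813 (also 0.813 with df 68 for one covariate and no variance gain). The stated 80% reproduces for one score. If all three scores were tested at 5% unadjusted, the chance of at least one false positive is 1 − 0.95³ = 14.3% if independent, and about 10% to 13% for assumed correlations of 0.8 to 0.3. With Bonferroni (0.05/3), power at N = 72 is 0.669.

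**3. Why one accuracy is not bias.** Equal-variance signal-detection model for a two-choice task, with sensitivity d' and criterion c (negative c means a bias towards answering negative):

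- negative accuracy = Φ(d'/2 − c); positive accuracy = Φ(d'/2 + c)
- error difference = rate of positive faces called negative minus rate of negative faces called positive

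| d' | c | Negative | Positive | Error difference |
|---|---|---|---|---|
| 1.5 | −0.2 | 82.9% | 70.9% | 12.0 points |
| 2.0 | −0.2 | 88.5% | 78.8% | 9.7 points |
| 1.5 | 0 | 77.3% | 77.3% | 0 |
| 2.0 | 0 | 84.1% | 84.1% | 0 |

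From row 1 to row 2 the criterion is unchanged, yet positive accuracy rises by 78.8 − 70.9 = 7.9 points. From row 1 to row 4 bias is removed, yet negative accuracy rises by 84.1 − 82.9 = 1.2 points, against Hypothesis 1.

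**4. Simulation.** Every value here is assumed, since the documents give none: between-person SD 0.5 for d' and 0.25 for c, intake-to-training correlation 0.6, 20 or 40 trials per valence. There are 24 per group, ANCOVA on intake, and two-sided 5% t tests against each control, both required. Unless noted, both controls stay at d' = 1.5, c = −0.2. Main scenarios used 4,000 runs, so the simulation standard error is at most √(0.5 × 0.5 / 4000) = 0.8 points. Entries are the share of simulated trials showing reduced bias, at 20 / 40 trials.

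| Mindful breathing against controls | Negative accuracy | Positive accuracy | Both agree | Error difference |
|---|---|---|---|---|
| No effect | 0.5% / 0.7% | 0.4% / 0.5% | – | 0.4% / 0.5% |
| Bias unchanged, d' +0.5 | 0% / 0% | about 30% / 43% | 0% | 1.1% / 1.4% |
| Same, one control gains 0.25 | – | about 11% / 15% | – | – |
| Same, one control gains 0.5 | – | about 1.5% | – | – |
| Bias unchanged, d' +0.25 | – | 5.7% / 8.6% | – | 0.6% / 1.1% |
| Bias removed, d' unchanged | 18.9% / 27.9% | 17.0% / 25.8% | about 3% / 7% | about 41% / 57% |
| Bias removed and d' +0.5 | 0.2% / 0.1% | 85.0% / 95.3% | 0.2% / 0.1% | 45.4% / 63.0% |

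In the second row negative accuracy is also significantly against Hypothesis 1 in 22.9% / 34.4%, which is the conflict for which the plan has no rule.

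**5. Scale.** For one arm shifted by δ SD against two equal controls, f = δ × √(2/9) = 0.47δ. A d' gain of 0.5 is 1 between-person SD (f = 0.47), above the plan's 0.38. A gain of 0.25 is f = 0.24. Removing a bias of 0.2 is 0.2/0.25 = 0.8 SD, about f = 0.38. These are on the underlying scale, before trial noise.

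**The case against.** A reader might infer that the EPBT has no neutral faces and that the measure cannot be computed. The documents do not support that. The EPBT sentence is an unfinished list introduced by examples, the numbering of the tasks around it skips an item, and Aim 1 mentions neutral faces twice. A category may have been dropped in editing. What stands is that the text leaves the matter unclear.

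A reader might also infer that the plan takes one accuracy alone as proof of reduced bias, and so carries a 30% to 43% false-claim rate. That is not stated either. Aim 1 pairs the two accuracies in one item, and Hypothesis 1 can be read as a joint pattern. In the model above, sensitivity moves both accuracies the same way and bias moves them in opposite ways, so a joint rule gives no false claims in the pure-sensitivity case. But the plan does not state a joint rule, and such a rule would have very little power.

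The 30% / 43% case is also the most favourable to the concern: the whole gain goes to one arm and exceeds the planned effect. The Habituation condition in Experimental Procedures shares the arousal monitoring and tone pairing of Mindful Breathing, and Aim 1 itself expects mindful breathing and perspective-taking to act alike in some respects. A shared gain shrinks the problem sharply. The cited background on sensitivity does not define signal-detection d'. The model is two-choice and does not simulate the neutral measure. All of this stands, and limits the figures to illustration.

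**Conclusion.** The concern holds in limited form and should be fixed before analysis. From the text alone, it is unclear whether the first-listed Aim 1 measure has trials at training or a matching intake value, it is unclear whether the BLERT is given at training, and no score or decision rule is attached to the 5% test. From the model, either accuracy read alone mixes bias with sensitivity. That direction does not depend on the assumed values, but the size does: for a 0.5 gain in d', false signals of reduced bias on positive accuracy range from about 1.5% to 43%, depending on whether a control gains too and on trial count. The power calculation is not in error; 80% reproduces, provided f = 0.38 applies to whichever score is named.

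**What to change.** 1. Reconcile Purpose of the Study, Measures and Tasks, Experimental Procedures and Specific Aims 1 and 2. State the EPBT face categories and answer options, and which tasks are given at each of the three sessions. If the EPBT has no neutral faces, drop the neutral measure from Aim 1. If only the EPBT is given at training, say that Aim 1 rests on it and that the BLERT enters Aim 2 at times 1 and 3.
2. Name one EPBT bias score combining both valences for the 5% test, in the planned ANCOVA with its intake value. One example is the rate of positive faces called negative minus the rate of negative faces called positive. Match the formula to the answer options. The signal-detection criterion suits a two-way answer only: with a neutral option, if correct answers fall from 80% to 70% on both valences and opposite errors stay at 10%, the criterion moves from −0.5 × (z(0.80) + z(0.10)) = 0.22 to −0.5 × (z(0.70) + z(0.10)) = 0.38, while the error difference stays at 0.
3. Report the single accuracies as secondary, along with the neutral-to-negative rate if it is kept and is not the named score. Report discrimination separately. Do not read lower negative-face accuracy alone as reduced bias.

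**Cost.** Mostly wording and scoring of answers already collected; the task lengthens only if neutral faces have to be added. With one named score, N = 72 and the stated power are kept. The combined score is less familiar, still shifts slightly with sensitivity (12.0 to 9.7 points above), and shrinks if neutral answers replace errors in a biased responder (errors of 20% and 10% halved move it from 10 to 5 points). It is also significant less often than positive accuracy when sensitivity rises as well (45% to 63% against 85% to 95%).

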## Data Analysis & Statistical Considerations

For the primary outcome of biases in emotion perception, the estimates were derived from a mean difference between conditions. With a Type-I error rate of 5% and 72 participants (24 per group), we will have at least 80% power to detect a medium to large effect size (Cohen's  $f = 0.38$ ), based on previous research demonstrating negative biases in emotion perception using similar behavioral measures. (Schmid & Schmid Mast, 2010) Because we anticipate a 10% to 15% rate of dropout, 30 participants will be randomized to each group. Therefore, this study will recruit 90 adult participants over the age of 18 who have high emotion dysregulation and interpersonal problems.

Since 2004, the CBTRP has recruited a range of adult psychiatric samples all characterized by problems with emotion regulation. Across studies of emotional functioning, it is estimated that our lab has run over 980 participants since 2004, at a rate of roughly 90 per year. In our previous NIMH project, over 33 months we have screened 1154 individuals and enrolled 169 participants, at a rate of 5.12 per month. We project enrolling 90 participants over 14 months, at a rate of 6.43 per month. Given our demonstrated track record of success meeting the required recruitment target in the present application, we expect to meet recruitment targets in the proposed project.

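### The stated 80% power is that of an omnibus three-group test, whereas Hypothesis 1 needs mindful breathing to beat both comparison arms, and the plan gives neither contrasts nor power for that

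*Combined protocol and SAP*

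**What the plan says.** All of the relevant text is in the combined protocol and SAP, under Data Analysis & Statistical Considerations.

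- **Power.** "With a Type-I error rate of 5% and 72 participants (24 per group), we will have at least 80% power"; the detectable effect is Cohen's f = 0.38. On its basis the section says only that "the estimates were derived from a mean difference between conditions". It does not say which conditions, whether f is adjusted for baseline, how the three means are arranged, or whether tests are one- or two-sided.
- **Size.** Thirty per group are randomised, allowing for 10% to 15% dropout. The power statement itself rests on 24 per group.
- **Planned test (Specific Aim 1).** ANCOVA of group differences on the laboratory tasks, adjusted for intake scores. No pairwise contrast or follow-up test is named.
- **Hypothesis 1 (Specific Aim 1).** Less bias under the intervention "compared to participants in both the control conditions", and then more explicitly: "we predict that the emotion regulation intervention would reduce this bias significantly more than both the worry and perspective-taking conditions".

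**The concern.** The hypothesis is a conjunction: mindful breathing must be significantly better than each of two comparators. A three-group test of group differences answers another question. It can be significant because mindful breathing beats only one comparator, or because the two comparators differ from each other. If mindful breathing were identical to one comparator and f were still 0.38, the omnibus test would keep its 81% power although Hypothesis 1 would be false.

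Two things are at stake. A reader may take the 80% as the chance of confirming Hypothesis 1, which it is not. And because no contrast is fixed in advance, the analyst must choose after the data are in how a significant F becomes a statement about both comparators.

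**Working it through.** **Inputs from the plan.** Alpha 5%, three equal groups, n = 24 each (N = 72), f = 0.38.

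**Assumptions, because the plan is silent.** Two-sided 5% for each contrast, pooled error, no covariate gain in the base case, one outcome measure. Both contrasts must succeed, so no alpha adjustment is applied between them.

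**Step 1: reproduce the plan's figure.** For the omnibus F test with 2 and 69 df, the noncentrality is N f² = 72 × 0.38² = 10.40 and the 5% critical value is 3.13. Power is **81.3%**, which agrees with the stated minimum of 80%. Other readings fit less well: a single 1-df contrast gives 88.9%, and a two-group t test with d = 2f = 0.76 gives 73.2%. The plan does not use the word omnibus; the label is inferred from the use of f and from this match.

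**Step 2: turn f into pairwise differences.** f² is the mean squared deviation of the three group means from their average, in SD units.

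- A, controls equal (0, d, d): f² = 2d²/9, so d = 3f/√2 = 0.806 for each contrast.
- B, evenly spaced (0, δ, 2δ): f² = 2δ²/3, so δ = f√1.5 = 0.465, and the far contrast is 0.931.
- C, near control a quarter of the way (0, D/4, D): f² = 78D²/432, so D = 0.894, and the near contrast is 0.224.

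**Step 3: power for both contrasts.** Each t statistic has noncentrality d√(n/2) = d√12. The two share the intervention mean and so have correlation 0.5. Simulation at n = 24 gives:

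| Pattern | Near contrast | Far contrast | Both |
|---|---|---|---|
| A | 78.6% | 78.6% | **67.0%** |
| B | 35.4% | 88.8% | **34.6%** |
| C | about 11.5% | 86% | **about 11%** |

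As a check on A, independent contrasts would give 0.786² = 61.8% and perfectly correlated ones 78.6%; 67.0% lies between. For fixed f, A is the most favourable pattern.

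**Step 4: sensitivity (power for both, A / B).**

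- One-sided 5%, n = 24: 78.6% / 47.5%.
- Dropout of 10% to 15% leaves 27 to 25.5 per group. With 26: 71.5% / 37.4%. With 27: 73.4% / 38.7%.
- All 90 retained: 78.9% / 42.6%.
- If f = 0.38 is unadjusted and the baseline correlation is ρ, the residual SD shrinks by √(1 − ρ²). At n = 24: ρ = 0.3 gives 72% / 38%; ρ = 0.5 gives 82% / 45%; ρ = 0.7 gives 95% / 61%. At n = 26: ρ = 0.4 gives 80% in A; ρ = 0.5 gives 85% / 48%.

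For scale, 80% power for both contrasts without a covariate gain would take about 31 completers per group (93 in all) in A and 74 per group (222) in B.

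**The case against.** The strongest reply is that nothing is miscalculated. The 80% is right for a three-group comparison, Cohen's f is the natural effect size for the ANCOVA that the plan describes, and the power paragraph never claims power for beating both arms. This stands: the defect is a missing figure and a missing test.

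It can also be said that the low figures ignore planned features. Baseline adjustment is planned, and at the anticipated dropout more than 24 per group would be analysed. This stands in part. With equal controls, an unadjusted f and a baseline correlation of 0.4 to 0.5, power for both contrasts reaches about 80% or more. But the plan states no correlation and does not say whether f is already adjusted, and evenly spaced means stay well short at those correlations. Specific Aim 1 itself allows that one comparator may act much like mindful breathing, which points towards the weaker patterns.

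A reader might also infer that the plan's reading of a null result, as a sign of stable deficits in emotion perception, rests on these low figures. The text does not support that. It requires the hypotheses to be unsupported and also the conditions not to differ significantly. A trial in which mindful breathing beats only one arm does not meet that condition. At n = 24 at least one of the two contrasts is significant in about 90% of trials under A or B. The power for both contrasts is therefore not the power behind that sentence.

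**Conclusion.** The concern holds as a mismatch between the power statement, the planned test and the hypothesis. The stated 80% reproduces as omnibus power (81.3%). Hypothesis 1 needs two contrasts to succeed, and at the stated n and f that has at most about 67% power, about 35% with evenly spaced means and about 11% with one control near the intervention. These values assume two-sided 5% contrasts and no covariate gain.

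It would be tempting to say that the design delivers only 35% to 67% power. The documents do not support that as a property of the design. The 67% is a ceiling only under the stated assumptions, the 35% is not a floor, and a favourable baseline correlation could bring the equal-controls case to about 80%. What can be said firmly is that the plan's 80% does not describe Hypothesis 1, and that the plan lacks the inputs needed to state the figure that does.

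**What to change.** 1. First reconcile the comparison arms. The Study Overview and the condition descriptions under Experimental Procedures name habituation and control. Purpose of the Study, Potential Benefits and Specific Aim 1 name perspective-taking and worry. The contrasts cannot be written until these passages agree.
2. In Specific Aim 1, make two pre-specified, baseline-adjusted ANCOVA contrasts the test of Hypothesis 1: mindful breathing against each comparison arm, both required at two-sided 5%. Because both must succeed, no alpha adjustment between the two is needed for a single outcome.
3. In the power paragraph, label the 80% as omnibus power. Add the power for both contrasts, with the assumed pattern of means and baseline correlation, and say whether f = 0.38 is adjusted for baseline.

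The cost is a change of wording and a stated power that will probably be less favourable. No extra participants are needed.
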